17.4.1.2 Sensitivity analyses primary estimand

Continuous endpoints, body weight, HbA_{1c} and insulin dose – multiple imputation – copy reference- retrieved data

These analyses are repeats of the primary analyses using the CR principle in place of the J2R principle, just as for the CR sensitivity analysis of the primary estimand of the primary objective.

Continuous endpoints body weight, HbA_{1c} and insulin dose – multiple imputation – jump to reference - retrieved data - tipping point

These analyses are repeats of primary analyses where subjects who prematurely discontinue from the IDegLira arm are assumed to have received a treatment inferior to IGlar or any other treatment received after premature treatment discontinuation. The extent of the inferiority will be gradually increased to evaluate at which point (penalty) IDegLira is no longer superior to IGlar.

Count endpoint hypoglycaemic episodes – multiple imputation – copy reference

This is a repeat of the primary analysis using the CR principle in place of the J2R principle. More specifically, in this analysis IDegLira subjects are assumed to have the event rate of the IDegLira arm prior to premature discontinuation and the event rate of IGlar after premature discontinuation. The method follows the multiple imputation J2R for count data above, but in the second step pre discontinuation rates are the respective groups rates whilst post discontinuation rate is the rate of comparator (IGlar).

Protocol
Trial ID: NN9068-4229
UTN: U1111-1168-9343

CONFIDENTIAL

Date: 20 November 2015 | Novo Nordisk
Version: 2.0
Status: Final

Count endpoint hypoglycaemic episodes – multiple imputation – jump to reference – tipping point

This is a repeat of the multiple imputation J2R above, now varying a penalty on the post discontinuation event rate until IDegLira is no longer superior to IGlar.

17.4.1.3 Primary statistical analyses secondary estimand

Continuous endpoints body weight, HbA_{1c} and insulin dose – MMRM

This is the same analysis as for the primary objective. For insulin dose baseline HbA_{1c} will be used as covariate.

Count endpoint hypoglycaemic episodes

Here the negative binomial model described above is simply applied to data as is.

17.4.1.4 Sensitivity analyses secondary estimand

Continuous endpoints body weight, HbA1c and insulin dose – multiple imputation – jump to reference – retrieved data

These analyses are identical to the primary analyses of the primary estimand and serve to evaluate the MAR assumption.

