5.4 Treatment after discontinuation of trial product

When discontinuing trial products, either prematurely or at V32 the subject should be switched to a suitable marketed product at the discretion of the investigator.

5.5 **Rationale for treatment**

IDegLira will be investigated in this trial to demonstrate efficacy and safety, when added to SGTL2i ± OAD in T2DM subjects, inadequately controlled on SGTL2i ± OAD. If a subject is treated with DPP4i these have to be discontinued at randomisation, as IDegLira cannot be combined with DPP4i.

IGlar has been chosen as comparator as it is currently a widely used basal insulin.

The TTT approach will be applied after randomisation in order to optimise glycaemic control throughout the trial.

All subjects in both arms will continue with SGTL2i ± OAD at pre-trial doses. In case of a safety concern the dose(s) may be reduced or temporarily interrupted at the discretion of the investigator. SGTL2i ± OAD treatment must follow the current locally approved label and any local recommendations present at the time of conducting the trial.

The duration of 26 weeks has been chosen to obtain a stabilised HbA_{1c} ensuring an adequate length of time of trial product at steady state.

Protocol Trial ID: NN9068-4229 UTN: U1111-1168-9343

EudraCT No.: 2015-001596-48

CONFIDENTIAL

Date: Version: Status: Page:

20 November 2015 | Novo Nordisk 2.0 Final

24 of 107

Trial population

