8.1.7 Premature discontinuation of trial product

Subjects discontinuing trial product prematurely due to any of the rescue criteria (see section 6.5), criteria for premature discontinuation of trial product (see section 6.4) or at subjects own will, should be called in for an EoT visit corresponding to V32 as soon as possible after discontinuation of trial product, FU1 must be scheduled 7 days (+3 days) after discontinuation of trial product and FU2 must be scheduled 30 days (+3 days) after discontinuation of trial product.

Once the two follow-up contacts after discontinuation of trial product are completed the subject should be contacted by phone every 4 weeks. Information on antidiabetic medication and information on potential major cardiovascular events (MACE) and any SAEs occurring since last contact must be collected and recorded in the eCRF. Phone contacts must be documented in the medical record and in the eCRF. The subject should finally come in for a V32A at week 26 to report MACE, SAEs, total daily insulin dose, use of other antidiabetic medication, and have body weight measured and a blood sample taken to measure HbA_{1c}, see flow chart (section 2).

Final drug accountability must be done once the subject has discontinued the trial product and the premature discontinuation must be recorded in the IWRS through a treatment discontinuation session.

The reason for the premature discontinuation of trial product must be recorded in the eCRF.

Protocol Trial ID: NN9068-4229 UTN: U1111-1168-9343

EudraCT No.: 2015-001596-48

CONFIDENTIAL

Date: Version: Status: Page:

20 November 2015 | Novo Nordisk 2.0 Final 35 of 107

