(V32A) from subjects prematurely discontinued from randomised treatment. To estimate this estimand for evaluation of non-inferiority of HbA_{1c}, a pattern mixture model approach³⁵ will be adopted. It mimics an ITT scenario where withdrawn and prematurely discontinued subjects from the investigational treatment (IDegLira) arm not having a week 26 measurement are assumed to be switched to a treatment inferior to comparator (IGlar) or any other treatment received after premature treatment discontinuation. This corresponds to a jump to reference (J2R) principle where a penalty in terms of the NI margin is added to withdrawn or prematurely discontinued subjects in the IDegLira arm. Observe that the J2R principle and use of retrieved (V32A) data in analyses will equalise treatment effects and in turn assay sensitivity in the non-inferiority setting may be jeopardized. The penalty of the non-inferiority margin³⁶ is to remedy this. Multiple copies (1000 copies) of the full dataset will be generated by imputing missing values based on estimated parameters for a subgroup of subjects in the trial. This will be done as follows:

- As a first step, all post-randomisation HbA_{1c} values for prematurely discontinued subjects in the investigational treatment group (IDegLira) not having retrieved (V32A) data are set to missing
- In the second step, intermittent missing values are imputed using a Markov Chain Monte Carlo (MCMC) method, in order to obtain a monotone missing data pattern. This imputation is done for each treatment group separately and 1000 copies of the dataset will be generated. Subjects from either group with retrieved (V32A) data will now have a non-missing data pattern
- In the third step, for each of the 1000 copies of the dataset, an ANOVA model with pre-trial OAD and region as factors, and baseline HbA_{1c} as covariate is fitted to the change in HbA_{1c} from baseline to first planned HbA_{1c} measurement visit after randomisation (V10) based on the control group (IGlar) and subjects with retrieved (V32A) data in the investigational group (IDegLira). The estimated parameters, and their variances, from this model are used to impute missing values at the first planned HbA_{1c} measurement visit after randomisation (V10) for subjects in both treatment groups, based on their pre-trial OAD, region and HbA_{1c} at baseline

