17.3.2 Sensitivity analyses primary estimand

Any marked difference between the primary statistical analysis and sensitivity analyses will be commented upon in the CTR.

MMRM - retrieved data

A mixed model for repeated measurement (MMRM) with an unstructured covariance matrix will be applied for the statistical analysis. The MMRM model accounts for missing data by an assumption of missingness at random. That is, the trajectory of treatment discontinued subjects is assumed to be as for those subjects on similar treatment that complete treatment. All observed and retrieved (V32A) data will be included in the analysis. Thus this model operates under a different assumption on missingness and includes more observed data. The latter implies that any treatment effect up until premature discontinuation is taken into account.

The MMRM model will include treatment, pre-trial OAD, region and visit as fixed factors and the corresponding baseline value as a covariate. Interactions between visit and all factors and the covariate are also to be included in the model. This model will be referred to as the standard MMRM model

Multiple imputation – copy reference– retrieved data – NI penalty

In this analysis withdrawn and prematurely discontinued subjects from the investigational treatment (IDegLira) arm not having a week 26 measurement are assumed to respond as if treated with a treatment inferior to comparator (IGlar) or any other treatment received after premature treatment discontinuation from the time of treatment discontinuation.

The analysis is similar to the primary analysis except that observed values for prematurely discontinued IDegLira subjects are not set missing (step 1 is left out). Observe that for IDegLira now only missing data after premature discontinuation are imputed by the sequential ANOVAs (step 3 to 5) and this principle is named copy reference (CR); intermittent missing data are imputed by MCMC (step 2). Thus this analysis is to include more observed values and applying the sequential ANOVAs at a later point in the visit structure. The latter implies that any treatment effect up until premature discontinuation is taken into account.

EudraCT No.: 2015-001596-48

CONFIDENTIAL

Date: Version: Status: Page:

20 November 2015 | Novo Nordisk 2.0 Final 76 of 107

Multiple imputation – jump to reference – retrieved data – NI penalty – tipping point

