17.3.3 Primary statistical analysis secondary estimand

MMRM

The secondary estimand for the primary objective is difference in change from baseline in HbA_{1c} after 26 weeks between T2DM subjects randomised to IDegLira and IGlar, both in combination with SGLT2i ± OAD, attributable to randomised treatment, if all randomised subjects had tolerated and adhered to treatment until week 26.

This analysis is a repeat of the standard MMRM this time leaving out retrieved (V32A) data.

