17.3.4 Sensitivity analyses secondary estimand

ANOVA – LOCF imputation

This analysis is an ANOVA with treatment, pre-trial OAD and region as factors and baseline value as covariate based on the FAS and with missing data imputed by LOCF.

17.4 **Secondary endpoints**

17.4.1 **Confirmatory secondary endpoints**

The confirmatory secondary endpoints of the trial are tested for superiority of IDegLira to IGlar.

Protocol		Date:	20 November 2015	Novo Nordisk
Trial ID: NN9068-4229	CONFIDENTIAL	Version:	2.0	
UTN: U1111-1168-9343		Status:	Final	
EudraCT No.: 2015-001596-48		Page:	77 of 107	

In order to control the overall Type I error, a hierarchical testing procedure will be used. If non-inferiority in glycaemic control (change from baseline in HbA_{1c}) is concluded in the primary statistical analysis of the primary estimand, testing proceeds down the following hierarchy as long as superiority at a given stage is confirmed based on the primary statistical analysis of the primary estimand:

- 1. Superiority in weight change
- 2. Superiority in number of treatment-emergent (severe or BG confirmed symptomatic) hypoglycaemic episodes
- 3. Superiority in glycaemic control (change from baseline in HbA_{1c})
- 4. Superiority in insulin dose (total daily dose [U])

The following paragraphs detail the hypotheses and statistical analyses of the confirmatory secondary endpoints.

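### Section 17.4.1.4 offers a repeat of the de facto primary analyses as a check of the MAR assumption behind the de jure MMRM, but that run changes the quantity estimated as well as the missing-data assumption

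*Protocol*

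**What the plan says.** Section 17 sets two estimands for each confirmatory endpoint: a primary, de facto one (the effect whether or not subjects stay on treatment) and a secondary, de jure one.

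- **De jure analysis.** For HbA1c, section 17.3.3 defines the target as the difference "if all randomised subjects had tolerated and adhered to treatment until week 26" and the method as MMRM: "This analysis is a repeat of the standard MMRM this time leaving out retrieved (V32A) data". Section 17.4.1.3 uses the same analysis for body weight, HbA1c and insulin dose. Section 17.3.2 states that the MMRM handles missing data under MAR.
- **Its sensitivity analysis.** Section 17.4.1.4 re-runs the jump-to-reference multiple imputation with retrieved data: "These analyses are identical to the primary analyses of the primary estimand and serve to evaluate the MAR assumption". Amendment 2 renames the method from jump to reference to unconditional and changes nothing else there.
- **The run being repeated.** Under step 1 in section 17.3.1, the post-randomisation values of "prematurely discontinued subjects in the investigational treatment group (IDegLira) not having retrieved (V32A) data are set to missing". Steps 3 to 5 impute from a model fitted to IGlar plus IDegLira subjects with V32A data. Step 6, the non-inferiority penalty, is left out for these endpoints. That is correct, because section 17.4.1 says: "The confirmatory secondary endpoints of the trial are tested for superiority of IDegLira to IGlar".
- **What V32A contains.** After stopping trial product, "the subject should be switched to a suitable marketed product at the discretion of the investigator" (section 5.4). V32A then takes place at week 26, "to report MACE, SAEs, total daily insulin dose, use of other antidiabetic medication" (section 8.1.7), together with weight and HbA1c.

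**The concern.** A sensitivity analysis for MAR should hold the target quantity and the observed data fixed and replace MAR with a stated alternative. The reader then learns how far the conclusion moves as the assumption is relaxed. The section 17.4.1.4 run changes the target as well. Someone comparing it with the MMRM cannot tell whether a gap reflects data missing not at random, or only that the effect of a treatment policy differs from the effect under full adherence. Agreement is also weak evidence, because the changes can offset one another.

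At stake is the robustness assessment of the de jure results. Section 17 rests inference on the primary analyses of the primary estimands, so no confirmatory decision depends on it.

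**Working it through.** **1. The two analyses side by side**

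| | De jure MMRM (17.3.3, 17.4.1.3) | Run in 17.4.1.4 |
|---|---|---|
| Estimand | Effect if all had adhered | Effect regardless of adherence |
| V32A data | Excluded | Included, taken after the switch to another product; for insulin dose it is the dose after that switch |
| On-treatment data before stopping | All used | Deleted for IDegLira discontinuers without V32A; kept for IGlar discontinuers |
| Missing values | MAR, own arm | Imputed from IGlar plus retrieved IDegLira subjects |

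**2. What other listed runs separate**

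- Copy reference (conditional) against jump to reference isolates step 1 (17.4.1.2).
- For HbA1c, the MMRM in 17.3.2, where "All observed and retrieved (V32A) data will be included in the analysis", against the MMRM without V32A isolates the retrieved data. No such pair is listed for weight or insulin dose.
- LOCF in 17.3.4 is one fixed alternative, for HbA1c only.
- Every tipping-point run (17.3.2, 17.4.1.2) is built on the de facto analysis. None varies MAR by degrees with the de jure estimand held.

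**3. Size, using body weight with MAR true**

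From the protocol: 208 per arm, a 1 kg effect, marginal power in the order of 75% (17.1), about 15% missing (17). The implied SD is

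1 / [(1.960 + 0.674) × √(2/208)] = 3.87 kg,

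and a t-test with this SD has power 0.748. The standard error is 3.87 × √(2/208) ≈ 0.38 kg.

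Assumed, not in the protocol: visits at weeks 4, 8, 12, 16, 20 and 26 follow the flow chart, but the correlation of 0.9 per 4 weeks, the constant effect over visits, the retrieval rate, the off-treatment behaviour and the dropout mechanism are assumptions. Dropout after each visit is logistic in the last observed weight change and calibrated to 15% per arm, so MAR holds by construction.

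Simplest case: stopping at random, nobody retrieved. The run gives 0.85 × (-1) + 0.15 × 0 = -0.85 kg against -1 kg from the MMRM, a difference of 0.15 kg with MAR true.

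Large-sample simulation, run minus MMRM in kg (Monte Carlo error about 0.01; negative favours IDegLira), true effect -1 kg. Paired entries: retrieved subjects keep none / all of the effect.

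| Dropout mechanism | 0% retrieved | 50% | 80% | 100% |
|---|---|---|---|---|
| At random | 0.14 | 0.15 / 0.07 | 0.15 / 0.03 | 0.15 / 0.00 |
| Higher weight change stops, odds ratio 1.65 per SD | -0.03 | 0.07 / -0.01 | 0.12 / 0.00 | 0.15 / 0.00 |
| Lower weight change stops, odds ratio 1.65 per SD | 0.32 | 0.24 / 0.16 | 0.18 / 0.06 | 0.15 / 0.00 |

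- Odds ratio 1.35, 0% retrieved: +0.04 (higher stops) and +0.26 (lower stops).
- No true effect, 0% retrieved: 0.00 at random; -0.10 and +0.11 at odds ratio 1.35; -0.18 and +0.18 at 1.65.
- No true effect, 50% retrieved, odds ratio 1.65, higher stops: -0.08.
- Correlation 0.7, odds ratio 1.35, 0% retrieved: +0.10 and +0.21 at -1 kg; -0.05 and +0.06 at no effect.

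A second simulation with correlation 0.8 and the effect lost off treatment gave about 0.15 kg under random stopping. With dropout depending on the last value it gave about 0.00, 0.07 and 0.13 kg at 0%, 50% and 100% retrieval. The two results can therefore differ when MAR is true, or agree because shifts cancel. The negative entries show that the run is not always the conservative one.

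**4. A run that keeps the estimand**

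Multiple imputation within the subject's own arm, on on-treatment data, agreed with the MMRM to within 0.003 kg at delta 0 under random stopping and odds ratio 1.65 in either direction. A delta on the 15% of IDegLira subjects imputed moves the estimate by 0.15 × delta, so with an estimate of -1 kg superiority is lost at

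delta = (1 - t × SE) / 0.15.

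- 208 per arm, SE 0.3796: (1 - 1.966 × 0.3796) / 0.15 = 1.69 kg
- 177 per arm (208 × 0.85), SE 0.4115: (1 - 1.967 × 0.4115) / 0.15 = 1.27 kg
- Trial-size imputation, SE 0.395 (correlation 0.9) and 0.410 (correlation 0.7): 1.49 and 1.29 kg

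**The case against.** **Reference-based imputation is a recognised stress test of MAR.** It is, when the estimand and the observed data stay as they were. Here both change.

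**No run can attribute a difference to MAR failing, and a delta run also departs from the MMRM when MAR is true.** Both statements are correct. MAR cannot be verified from observed data, so a non-zero difference is not in itself the defect. The defect is that the quantity estimated is not held fixed. A delta run departs from the MMRM by a known amount, for a stated reason, on the same quantity.

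**The retrieved data and the imputation model are simply how the de facto estimand is estimated, so the changes are really one.** Largely fair, but that one change is the change of estimand. The deletion in step 1 can be separated, since copy reference omits it.

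**The extremes need 0% V32A retrieval.** Both ends of the quoted range do. At 80% retrieval and an effect of -1 kg the range is 0.00 to 0.18 kg. However, the shift towards IDegLira is still -0.08 kg at 50% retrieval with no true effect.

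**HbA1c is better covered, and further sensitivity runs may sit in the SAP.** HbA1c does have LOCF and the MMRM pair, so the gap is widest for weight and insulin dose. The point here is not a missing analysis: the protocol itself assigns this purpose to this run.

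**Nothing is decided on it.** Agreed, and the rating reflects that.

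**Conclusion.** The concern holds and is minor. The purpose stated in section 17.4.1.4 is not one the named analysis can serve, because it moves from the de jure to the de facto estimand together with the missing-data assumption. With MAR true, the difference for body weight ran from about -0.18 to +0.32 kg over the assumed scenarios, always below one standard error (about 0.38 kg). A difference is not inevitable and its sign is not fixed. These sizes rest on the assumptions listed and on an SD derived from an approximate power figure; the logical point rests on none of them. Confirmatory tests, type I error and sample size are unaffected.

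**What to change.** In section 17.4.1.4:

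1. Keep the existing run, but describe it as a comparison of the de jure with the de facto result and drop the claim that it evaluates MAR.
2. Name as the MAR sensitivity analysis a run that keeps the de jure estimand: on-treatment data only, without V32A; multiple imputation under MAR within the subject's own arm; then an increasing unfavourable delta added to imputed IDegLira values until superiority is lost. Report that delta for each of the three endpoints.

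The same approach could be added to section 17.3.4 beside LOCF for non-inferiority. The cost is one reworded sentence and a few extra analysis runs, with no new data and no change to the confirmatory tests.

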17.4.2 Supportive secondary endpoints

The supportive secondary endpoints will be addressed in terms of the primary estimand only.

17.4.2.1 Efficacy endpoints

HbA_{1c} responder after 26 weeks (yes/no)

Two dichotomous endpoints (responder=yes/non-responder=no) will be defined based on whether a subject has met a specific target level after 26 weeks:

- $HbA_{1c} < 7.0 \%$
- $HbA_{1c} \le 6.5 \%$

Analysis of each the two responder endpoints will be based on a logistic regression model with treatment, pre-trial OAD and region as fixed factors and baseline HbA_{1c} value as a covariate, hereafter referred to as the standard logistic regression model.

For each of the multiple copies (1000) of the full dataset of the primary analysis of the primary estimand (multiple imputation J2R with retrieved data, NI penalty section 17.3.1) the responder endpoints are derived without using the non-inferiority penalty (step 6) and analysed with the standard logistic regression model. Estimates are pooled using Rubin's rule.

Protocol
Trial ID: NN9068-4229
UTN: U1111-1168-9343

Date: 20 November 2015 | Novo Nordisk
Version: 2.0
Status: Final

Page:

81 of 107

HbA_{1c} responder endpoints without weight gain after 26 weeks

EudraCT No.: 2015-001596-48

Responder for HbA_{1c} without weight gain after 26 weeks will be defined as

- HbA_{1c} < 7.0% and change in body weight from baseline ≤ 0 kg
- HbA_{1c} \leq 6.5% and change in body weight from baseline \leq 0 kg

Theses endpoint will be analysed as the HbA_{1c} responder endpoints, now using also the multiple copies of the full dataset for weight (section $\underline{17.4.1}$), and including baseline weight too as covariate in the standard logistic regression model.

HbA_{1c} responder endpoints without treatment-emergent severe or BG confirmed symptomatic hypoglycaemic episodes after 26 weeks

Responder for HbA_{1c} without treatment-emergent severe or BG confirmed symptomatic hypoglycaemic episodes after 26 weeks will be defined as

- HbA_{1c} < 7.0% and without treatment-emergent severe or BG confirmed symptomatic hypoglycaemic episodes during the last 12 weeks of treatment
- HbA_{1c} \leq 6.5% and without treatment-emergent severe or BG confirmed symptomatic hypoglycaemic episodes during the last 12 weeks of treatment

Theses endpoints will be analysed as the HbA_{1c} responder endpoints, where subjects with less than 12 weeks of treatment conservatively will be set to being non-responder.

HbA_{1c} responder endpoints without treatment-emergent severe or BG confirmed symptomatic hypoglycaemic episodes and weight gain after 26 weeks

Responder for HbA_{1c} without treatment-emergent severe or BG confirmed symptomatic hypoglycaemic episodes and weight gain after 26 weeks will be defined as

- HbA_{1c} < 7.0%without treatment-emergent severe or BG confirmed symptomatic during the last 12 weeks of treatment, and change in body weight from baseline \leq 0 kg
- HbA $_{1c} \le 6.5\%$ without treatment-emergent severe or BG confirmed symptomatic during the last 12 weeks of treatment, and change in body weight from baseline ≤ 0 kg

Theses endpoints will be analysed as the composite HbA_{1c} and weight responder endpoints, where subjects with less than 12 weeks of treatment conservatively will be set to being non-responder.

Waist circumference change from baseline after 26 weeks

Change from baseline in waist circumference will be analysed by multiple imputation J2R.

Fasting plasma glucose change from baseline after 26 weeks

Change from baseline in FPG will be analysed by multiple imputation J2R.

CONFIDENTIAL

Date: Version: Status: Page:

20 November 2015 | Novo Nordisk 2.0 Final 82 of 107

Fasting lipid profile after 26 weeks

Cholesterol, LDL cholesterol, HDL cholesterol, VLDL cholesterol, triglycerides and free fatty acids will be analysed separately by multiple imputation J2R. In these statistical analyses, the endpoint will be log-transformed and so will the corresponding baseline covariate.

Self-measured plasma glucose (SMPG) 9-point profile change from baseline after 26 weeks

The following six endpoints from the 9-point SMPG profile will be defined:

- 9-point profile (individual SMPG values). [One endpoint]
- Mean of the 9-point profile, defined as the area under the profile (calculated using the trapezoidal method) divided by the measurement time. [One endpoint]
- Prandial plasma glucose increments (from before meal to 90 min after meal for breakfast, lunch and dinner). The mean increment over all meals will be derived as the mean of all available meal increments. [Four endpoints]

A linear mixed effect model will be fitted to the 9-point SMPG profile data. The model will include treatment, pre-trial OAD, time (within 9-point profile), the interaction between treatment and time, the interaction between pre-trial OAD and time as fixed factors, and subject as random effect. From the model mean profile by treatment and relevant treatment differences will be estimated and explored.

Change from baseline in mean of the 9-point profile and prandial increment endpoints will be analysed separately by multiple imputation J2R.

Blood pressure (systolic and diastolic) change from baseline after 26 weeks

Change from baseline in systolic and diastolic blood pressure will be analysed separately by multiple imputation J2R.

